9.6.5 Sensitivity Analysis

Sensitivity analysis centred around the robustness of results to assumptions of the study design and availability of key data elements may include the following:

- If the risk window is not well known, conduct analyses with alternative risk intervals and/or washout periods between the risk and comparison windows
- Incorporate a more sensitive case definition by including both confirmed and probable cases
- If exact dates of events are unknown and some are imputed (e.g., if the onset of the event could be prior to date assigned by case validation), conduct analyses surrounding assumptions used to set the event date
- If time-varying confounders are not fully available in all sites, restrict the analysis to sites where data are available on these time-varying confounders
- If the outcome affects the likelihood of exposure and/or the no exposure information is collected after the hospital visit associated with the outcome, consider using Farrington et al’s pseudolikelihood approach [7]

9.7 Quality Control

Standard operating procedures or internal process guidance at each research centre will be used to guide the conduct of the study. These procedures may include internal quality audits, rules for secure and confidential data storage, methods to maintain and archive project documents, quality control procedures for programming, and standards for writing analysis plans.

This section will describe the study-specific process for programming quality control (e.g., independent programming and/or review of summary output and programming logs by a second programmer), and procedures for data storage, archiving, and backup at each study centre. Also described will be processes for review and quality control of study documentation and reporting of pooled results across research centres.

9.8 Limitations of the Research Methods

The study is subject to limitations due to both the study design and use of clinical data and other data not collected for research purposes. The major limitation of self-controlled designs and their variants is that they are only suited to study outcomes with a short induction period and an abrupt onset. These designs are not appropriate for assessing outcomes with gradual onset or a long induction period.

Other limitations of self-controlled designs and their variants (including the vaccinated case-coverage design as proposed in this template) include the possibility that incorrectly specifying the risk window will lead to biased incidence rate ratio/odds ratio estimates. If the risk window is not well characterised based on prior data or studies, sensitivity analyses with alternative risk interval definitions should be undertaken. Other

study design approaches that are less susceptible to this source of bias (for example, a cohort design with historical comparators or a traditional cohort design) could also be used as complimentary approaches, as appropriate. Another limitation of the SCRI and CCO is that they are susceptible to bias due to time-varying confounders such as infections. While attempts to collect and adjust for time-varying confounders will be made, not all data sources will have information on them. A major limitation of the CCO is that it should not be used if there are temporal trends in exposure. While the vaccinated case-coverage design addresses potential bias due to time trends in exposure, it assumes that the temporal trends in exposure are the same in cases as they are in the reference population. Another limitation is that it requires information on the number of persons vaccinated on a daily basis, stratified by subgroups of important confounders; it is anticipated that this information will not be available for populations of interest for the catchment areas of all hospital sites. Finally, the vaccinated case-coverage design is that it may have less statistical power than the CCO and the SCRI designs, as cases for whom nearly everyone or no one is vaccinated during the risk window are uninformative for the analysis.

Data related limitations include that the study will depend on the accuracy of codes and algorithms to identify outcomes, and the availability of records to confirm outcomes. Misclassification of outcome (both events and dates of events) will be minimised by conducting validation. However, the use of medical record and other secondary data sources for validation purposes may limit the ability to apply Brighton Collaboration criteria and other standardised case definitions to confirm outcomes and to identify true onset of the outcomes.

Exposure ascertainment may be based on pharmacy dispensing records, general practice records, vaccination registers, medical records, vaccination cards, or other data sources. The validity of coding for COVID-19 vaccines and dates of vaccination are currently unknown. Additionally, it is unknown whether coding will distinguish between specific products of COVID-19 vaccines.

9.9 Other Aspects

This section, which is optional, will contain information on any other aspect of the research method not covered by previous sections, such as scientific advisory board or endpoint adjudication committees.

10 Protection of Human Subjects

This is a non-interventional study using secondary data collection and does not pose any risks for patients. All data collected in the study will be deidentified with no breach of confidentiality with regard to personal identifiers or health information. Each hospital research partner will apply for an independent ethics committee review according to local

regulations. Data protection and privacy regulations will be observed in collecting, forwarding, processing, and storing data from study participants.

11 Management and Reporting of Adverse Events/Adverse Reactions

For studies in which the research team uses data from automated health care databases only, according to the International Society for Pharmacoepidemiology (ISPE) [10] Guidelines for Good Pharmacoepidemiology Practices (GPP),

Aggregate analysis of database studies can identify an unexpected increase in risk associated with a particular exposure. Such studies may be reportable as study reports, but typically do not require reporting of individual cases. Moreover, access to automated databases does not confer a special obligation to assess and/or report any individual events contained in the databases. Formal studies conducted using these databases should adhere to these guidelines.

For non-interventional study designs that are based on secondary use of data, such as studies based on medical chart reviews or electronic health care records, systematic reviews or meta-analyses, reporting of adverse events/adverse drug reactions is not required. Reports of adverse events/adverse drug reactions should only be summarised in the study report, where applicable [11].

According to the EMA Guideline on Good Pharmacovigilance Practices (GVP), Module VI – Management and Reporting of Adverse Reactions to Medicinal Products [11],

"All adverse events/reactions collected as part of [non-interventional post-authorisation studies with a design based on secondary use of data], the submission of suspected adverse reactions in the form of [individual case safety reports] is not required. All adverse events/reactions collected for the study should be recorded and summarised in the interim safety analysis and in the final study report."

Module VIII – Post-Authorisation Safety Studies, echoes this approach [1]. The new legislation further states that for certain study designs such as retrospective cohort studies, particularly those involving electronic health care records, it may not be feasible to make a causality assessment at the individual case level.

12 Plans for Disseminating and Communicating Study Results

In its Guidelines for GPP, ISPE contends that "there is an ethical obligation to disseminate findings of potential scientific or public health importance" [10]; for example, results pertaining to the safety of a marketed medication. "...[T]he marketing

authorisation holder should communicate to the Agency and the competent authorities of the Member States in which the product is authorised the final manuscript of the article within 2 weeks after first acceptance for publication.”

Study results will be published following guidelines, including those for authorship, established by the International Committee of Medical Journal Editors [12]. When reporting results of this study, the appropriate Strengthening the Reporting of Observational Studies in Epidemiology (STROBE) checklist will be followed [13].

Communication via appropriate scientific venues will be considered.

[To be completed or modified by study investigator(s), as needed.]

13 Other Good Research Practice

This study will adhere to the *Guidelines for GPP* [10] and has been designed in line with the European Network of Centres for Pharmacoepidemiology and Pharmacovigilance (ENCePP) *Guide on Methodological Standards in Pharmacoepidemiology* [14]. The *ENCePP Checklist for Study Protocols* [15] will be completed (see Annex 2).

The study is a postauthorisation study of vaccine safety and will comply with the definition of the non-interventional (observational) study referred to in the International Conference on Harmonisation of Technical Requirements for Registration of Pharmaceuticals for Human Use tripartite guideline *Pharmacovigilance Planning E2E* [16] and provided in the EMA *Guideline on Good Pharmacovigilance Practices (GVP) Module VIII: Post-Authorisation Safety Studies* [1], and with the 2012 European Union pharmacovigilance legislation, adopted 19 June 2012 [17]. The study will comply with the study reporting requirements specified in Module VIII section VIII.B.6.3.1. “Progress reports” and VIII.B.6.3.2. “Final Study Report” of the *Guideline of Good Pharmacovigilance Practices* [1].

Annex 1. List of Stand-Alone Documents

Number	Document Reference Number	Date	Title
1		<<MM.DD.YYYY>>	
2		<<MM.DD.YYYY>>	
3		<<MM.DD.YYYY>>	
4		<<MM.DD.YYYY>>	

Annex 2. ENCePP Checklist for Study Protocols

GVP. A copy of the ENCePP Checklist for Study protocols available at http://www.encepp.eu/standards_and_guidances/index.html completed and signed by the main author of the study protocol should be included in Annex 2.

The checklist will facilitate the review of the protocol and evaluation of whether investigators have considered important methodological aspects.

In question 9.5 of the Checklist, Revision 1:

“Study start” means “Start of data collection”

“Study progress” means “Progress report(s)”

“Study completion” means “End of data collection”

[figure not shown]
“Reporting” means “Final report of the study results”

Annex 3. Overview of Self-controlled Risk Interval Design, Case-Crossover Design, and Vaccinated Case- coverage Design

Self-controlled Risk Interval Design

The SCRI design (Figure 3-1) is a variant of the SCCS and builds upon the conceptual framework of the cohort study, with exposure history fixed and events random [3-5]. In the pandemic setting when providing timely results is key, a SCRI design is particularly helpful because it shortens the observation period, as compared with the traditional SCCS. The SCRI design uses information only from vaccinated persons identified during the study period and compares the incidence of adverse events within periods of time hypothesised to be at increased risk due to exposure (“risk window”) with incidence during a self-matched control window [4] Although the study population includes all patients receiving vaccines, only vaccinees with events occurring during either the risk or control window are informative for the analysis.

Figure 3-1. Self-controlled Risk Interval Design

Note: In this example, the risk interval is 1 to 42 days after vaccination, and the control interval is 51 to 92 days after vaccination.

Control windows may be before or after vaccination and are typically a fixed length between individuals, although they are not required to be the same length as the risk window. This control period serves as an estimate of the baseline incidence. Unlike the traditional cohort study, the SCRI design does not censor follow-up at an event. These designs are well suited to study single or multiple exposures and independent recurrent events or rare non-recurrent events. However, if an event is recurrent but each occurrence is not independent of one another (e.g., stroke, myocardial infarction), then the analysis should be limited to the first event.

In a hospital-based study, the SCRI design would be operationalised by first identifying patients who have been treated and/or diagnosed with the outcomes of interest at hospital sites (regardless of vaccination status). Among the cases, vaccinations and date of vaccinations would then be identified. This approach has important study design and methodological implications because only exposures that occur before the outcome will be available for analysis, unless it is feasible to collect exposure information following hospital discharge. A SCRI design with a pre-vaccination control interval could be considered if it is feasible to collect exposure information following hospital discharge, as

this would enable the inclusion of outcomes that occur before exposure; to use this approach, the outcome should not be a contraindication to exposure. The use of a pre-vaccination control interval would provide more timely results than a postvaccination control window, as data must fully accrue through the end of follow-up for each dose before it can be included in analyses. However, it is anticipated that information on exposures may not be available after hospital discharge to the end of the study period, as was the case in a proof-of-concept study conducted by the World Health Organization (WHO) Global Vaccine Safety: Multi Country Collaboration [21]. Therefore, subsequent discussion of the SCRI in this document will describe the use of a postvaccination control interval, which would not require collection of exposure information following hospital discharge.

Similar to the SCRI, the CCO is a case-based study in which each person serves as his or her own control. However, the primary distinguishing feature of the two designs is that the CCO follows the conceptual framework of the case-control study, with events fixed and exposure random [4,22]. The design compares the odds of exposure in a window, during which it is hypothesised to trigger the adverse event to that in a control period, which represents the baseline odds of exposure. The study design is traditionally unidirectional, with the comparison window preceding the risk window in time, so as to avoid bias due to reverse causation (Figure 3-2). Only cases vaccinated in either the exposure or comparison window (not both windows) are informative for the analysis. Therefore, follow-up after events (i.e., hospital discharge) is not needed. The design is well suited to study single or multiple exposures as well as rare events.

Like the SCRI, the CCO can adjust for time-varying confounders if the appropriate data are available. However, unlike the SCRI, the CCO is biased if there are temporal trends in exposure. It is highly plausible that a person's likelihood of COVID-19 vaccination will change over time, as the vaccine will be new and likely highly desirable, and availability and vaccine recommendations may change over time. Additionally, the CCO may be subject to within-person protopathic bias and confounding by indication (or contraindication) if prodromal signs of the outcome prior to diagnosis of the event cause (or prevent) vaccination.

Figure 3-2. Case-Crossover Study Design

T = time in days.

Note: In this example, the risk window is 1 to 42 days before the adverse event.

Vaccinated Case-Coverage Design

A proposed variation of the case-coverage design, a vaccinated case-coverage design, is included as a candidate study design in this protocol template to adjust for temporal trends in exposure that may be present in a CCO design. The case-coverage design in its original form is analogous to logic of a case-control design and uses data from cases of the outcome under study and an external reference population, the latter of which is used to estimate the baseline odds of vaccination at the aggregate level. The case-coverage design can be matched on time to account for differences in vaccination coverage over time such that it compares the odds of vaccination in the exposure window for each case to the odds of vaccination during the same time period as the case's exposure window in an external reference population [23].

Similar to a traditional case-coverage design that is matched on calendar time, the vaccinated case-coverage design will compare the odds of vaccination in the exposure window for each case to the odds of vaccination during the same time period as the case's exposure window in an external reference population. However, unlike the traditional case-coverage design, the vaccinated case-coverage design will require that individuals be vaccinated during the observation period to be included. Like the CCO design, exposure and comparison windows preceding case onset date will be defined in cases; cases vaccinated in either the exposure or comparison window will be informative for analysis. To calculate the expected odds of vaccination in the exposure window for each case, the stratum comprising all individuals in the reference population who were similar to each case (e.g., of the same age, sex, and risk group) will be identified on the day of developing the outcome, and the odds of vaccination within the time period equating to the case's exposure window will be calculated. Individuals in the stratum of the reference population must have been vaccinated during calendar periods equating to the exposure or comparison windows before the onset of the case. Matching on calendar time accounts for differences in propensity to be vaccinated over time.

The vaccinated case-coverage design is predicated on the assumption that vaccination trends over time in the reference population reflect that of the cases. Bias due to the absence of this assumption should be minimised by matching cases to the reference population on important characteristics that are associated with the outcome and that may affect timing of vaccination (e.g., age or chronic conditions).

An anticipated challenge of the vaccinated case-coverage design in hospital-based studies is that it is likely to be difficult to identify appropriate data sources to estimate temporal trends in vaccination among groups of vaccinees defined by key confounders in catchment areas for participating hospitals; data on the number of vaccinations by calendar day and important risk factors are needed to implement this approach. Such data may come from population-based immunisation registers or other secondary data sources that capture vaccine coverage over time in samples representative of the target population.

Other Study Designs Considered but Excluded From This Template

The traditional SCCS was considered for inclusion in this template, but it has been excluded because it would require longitudinal data on vaccinations both before and after adverse events occur (i.e., both before and after hospital discharge) during the full study period. It is anticipated that this will not be possible without the use of immunisation registers, which are not available in many settings. Additionally, the SCCS provides less timely results than the SCRI because it requires a longer observation period in cases to accrue than the SCRI.

**Annex 4. Preliminary Assessment of Suitability of the
SCRI, CCO, and Vaccinated Case-Coverage
Designs to Study AESIs**

Table 4-1. Preliminary Assessment of the Suitability of the SCRI, CCO, and Vaccinated Case-Coverage Designs, by Study Outcome

Outcome	Suitability of SCRI (With Postvaccination Control Window)	Suitability of the CCO/Vaccinated Case-Coverage Design	Notes
Enhanced disease following immunisation	X	X	Requires unvaccinated comparator to identify whether disease is “enhanced” following vaccination
Multisystem inflammatory syndrome in children	✓	✓	
Acute respiratory distress syndrome	✓	✓	
Acute cardiovascular injury, including microangiopathy, heart failure, stress cardiomyopathy, coronary artery disease, arrhythmia	✓	✓	
Coagulation disorder, including deep vein thrombosis, pulmonary embolus, cerebrovascular stroke, limb ischaemia, haemorrhagic disease	✓	✓	
Generalised convulsion	✓	✓	
Guillain Barré Syndrome	✓	✓	
Diabetes (type 1 and unspecified type)	X	X	Has gradual onset and long latency
Acute kidney injury	✓	✓	
Acute liver injury	✓	✓	
Anosmia, ageusia	X	X	Not typically captured in hospital (unless accompanied by other illnesses requiring treatment in hospital)
Chilblain-like lesions	✓	✓	
Single organ cutaneous vasculitis	✓	✓	
Erythema multiforme	✓	✓	

Outcome	Suitability of SCRI (With Postvaccination Control Window)	Suitability of the CCO/Vaccinated Case-Coverage Design	Notes
Anaphylaxis	✓	✓	If the vaccine is given in more than one dose, the impact of bias in the SCRI design due to the potential interference of the outcome on subsequent vaccination could be explored using Farrington’s pseudolikelihood method for censored, perturbed, or curtailed postevent exposures [7].
Death (any cause)	✓	✓	Bias due to the interference of the outcome on subsequent vaccination in the SCRI design should be accounted for using Farrington’s pseudolikelihood method for censored, perturbed, or curtailed postevent exposures [7].
Sudden death	✓	✓	Bias due to the interference of the outcome on subsequent vaccination in the SCRI design should be accounted for using Farrington’s pseudolikelihood method for censored, perturbed, or curtailed postevent exposures [7].
Acute aseptic arthritis	✓	✓	
Meningoencephalitis	✓	✓	
Acute disseminated encephalomyelitis	✓	✓	

Outcome	Suitability of SCRI (With Postvaccination Control Window)	Suitability of the CCO/Vaccinated Case-Coverage Design	Notes
Narcolepsy	X	X	Diagnosis may be delayed, and some symptoms may occur consecutively over a long time period, which makes the onset of symptoms difficult to determine retrospectively
Thrombocytopenia	✓	✓	
Transverse myelitis	✓	✓	
Preterm birth	X	X	Risk window cannot be defined
Major congenital anomalies	X	X	SCRI not feasible because date of onset is unknown; CCO/vaccinated case-coverage design is not recommended because there may be time trends in vaccination with respect to both calendar time and gestational age, and it is anticipated to be difficult to obtain vaccine coverage rates on both time scales concurrently
Microcephaly	X	X	SCRI not feasible because date of onset is unknown; CCO/vaccinated case-coverage design is not recommended because there may be time trends in vaccination with respect to both calendar time and gestational age, and it is anticipated to be difficult to obtain vaccine coverage rates on both time scales concurrently
Fetal growth restriction	X	X	Risk window is unknown

Outcome	Suitability of SCRI (With Postvaccination Control Window)	Suitability of the CCO/Vaccinated Case-Coverage Design	Notes
Gestational diabetes	X	X	Risk window is unknown and date of onset is unknown
Preeclampsia	X	X	Risk window is unknown
Spontaneous abortion	X	X	Risk window is unknown
Stillbirth	X	X	Risk window is unknown
Induced abortion	X	X	Risk window is unknown
Termination of pregnancy for fetal anomaly (TOPFA)	X	X	Risk window is unknown
Neonatal death	X	X	Risk window is unknown
Maternal death	X	X	Risk window is unknown

CCO = case-crossover; SCRI = self-controlled risk interval.

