 - For persons who receive only one dose, define the risk and control intervals as 1 to 42 and 43 to 127 days after vaccination, respectively.
 - In the above scenarios, the control window could be placed even further in time from vaccination to incorporate a washout period between the risk and control intervals, as needed.
- If there is a short interval between doses of the vaccine but the risk interval is short, a dose-level analysis (treating each dose as a separate observation) could be conducted, but care must also be taken to ensure that the control interval does not overlap with the next dose. For example, suppose the vaccine is administered in two doses approximately 28 days apart, and the outcome of interest has a risk interval of 0 to 7 days. The control interval would need to end before 27 days after vaccination (e.g., 8-15 days) to ensure that there is no overlap of the control interval of the first dose with the risk interval of the second dose.

If the outcome affects the likelihood of a subsequent vaccination after the first dose, the impact of this potential bias could be explored in a sensitivity analysis using Farrington’s pseudolikelihood method for perturbed, censored, or curtailed observation periods for postevent exposures [7].

CCO Design

If the CCO design is used, an exposure window preceding the event will be selected to reflect the period during which exposure to COVID-19 vaccination is hypothesised to trigger the adverse event of interest. A single comparison window preceding the risk window will be selected to reflect the baseline prevalence of exposure; the comparison window should be selected independently of exposure status. Multiple comparison windows per case may also be considered but are not recommended because they may increase the potential for bias due to time-varying confounding and temporal trends in

exposure. By convention, the exposure window will index on the date of the adverse event, which will be time = 0. A washout period between the exposure and comparison windows can be implemented to avoid any carryover effects of the vaccine between the two windows.

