Both infections and receipt of other non-COVID-19 vaccines may act as confounders if they increase the risk of the adverse event of interest. Infections relevant to the adverse event of interest (e.g., SARS-CoV-2, influenza-like illness, upper respiratory infection, gastrointestinal infection) will be captured using diagnosis codes in hospital data and primary care data, if feasible. It is anticipated that not all hospitals will be able to collect information regarding individual-level infections for adjustment in the SCRI design because they will not be able to capture information after discharge, and any data obtained directly from primary care providers may require informed consent from patients. Vaccines relevant to the adverse event of interest will be captured in pharmacy dispensing records, general practice records, immunisation registers, medical records, vaccination cards, or other secondary data sources.

Both the SCRI and CCO can adjust for infections and receipt of other non-COVID-19 vaccines. In the SCRI, this is done by categorising the entirety of follow-up time into “exposed” and “unexposed” person-time with respect to infection or vaccination; each infection and non-COVID-19 vaccine will have its own risk window based on the temporal effect of the infection/vaccine on the outcome of interest. In the CCO, infection and vaccine status (yes vs. no) will be assessed separately during the risk and control windows for COVID-19 vaccination.

Vaccinated Case-Coverage Design

The vaccinated case-coverage design is not self-controlled and may be biased if time trends in exposure for calculating the expected odds of vaccination in the exposure window is not the same in cases and in the reference population. Adjustments for any such confounders will be made by matching cases to the reference population on the status of the confounder (e.g., age and sex), as of the case’s index date. To do this, the risk stratum for calculating the expected odds of vaccination in the exposure window for each case will need to be defined accordingly.

[Investigator should add confounders relevant to specific adverse events in this section and provide operational definitions].

Effect Modifiers

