9.6.2 Measures of Association

If the SCRI is used, conditional Poisson regression (conditioned on the individual) will be used to estimate incidence rate ratios and 95% confidence intervals for each outcome, with logarithm of time in each interval as the offset. If the CCO is used, conditional logistic regression (conditioned on the individual) will be used to estimate odds ratios and 95% confidence intervals for each outcome.

For the SCRI and CCO, time-varying confounders will be adjusted for in regression models. If applicable, in the SCRI, age and calendar time may be categorised into several categories, or treated as polynomial functions, with or without the use of splines in regression models. Both unadjusted and adjusted incidence rate ratios, by site and pooled across all sites, will be reported.

If the vaccinated case-coverage design is used, a logistic regression model will be fit for each AESI under study using separate summarised data sets. The data set for each AESI under study will have one record per risk set (i.e., case), with the outcome indicating whether vaccination occurred in the case's exposure or comparison window. The logarithm of the expected odds (i.e., logit) of vaccination inside the exposure window will be entered into the model as an offset term. For each case, this expected probability of vaccination inside the exposure window will be obtained from the reference population, as described in Annex 3. The model will include only an intercept with no covariate, with the following general form.

$$\text{Logit}(p_1) = \text{logit}(p_0) + \beta_0,$$

where p_1 is the observed probability of vaccination inside the exposure window among cases, p_0 is the expected probability of vaccination inside the exposure window among cases (based on vaccination data in the reference population), β_0 is the intercept; by exponentiating this coefficient, one obtains an odds ratio describing the association between vaccination and the outcome of interest occurring inside the risk interval.

Of note, the logistic regression model drops all cases for whom the expected probability of vaccination inside the exposure window is 0 or 1 (i.e., either everyone or no one is vaccinated inside the risk interval amongst the reference population), as these cases are noninformative.

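### Table 4-1 clears MIS-C and ARDS for all three designs without a caveat, although vaccine protection building up between the risk and reference windows can raise the null estimate above 1

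*Protocol*

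**What the plan says.** Annex 4, Table 4-1 ticks "Multisystem inflammatory syndrome in children" and "Acute respiratory distress syndrome" for the SCRI and for the CCO/vaccinated case-coverage designs, and leaves the notes column empty for both. The criteria in Table 1 cover place of treatment, latency, onset, risk period, effect of the outcome on vaccination, recurrence and vaccination trends. None concerns an outcome caused by the infection that the vaccine is meant to prevent.

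The windows are illustrated in three places:
- Annex 3, Figure 3-1 (SCRI): "In this example, the risk interval is 1 to 42 days after vaccination, and the control interval is 51 to 92 days after vaccination".
- Section 9.2.5.3 (SCRI, one dose): "define the risk and control intervals as 1 to 42 and 43 to 127 days after vaccination, respectively".
- Section 9.2.5.3 (CCO): an exposure window of 1 to 21 days and a comparison window of 50 to 70 days before the event. Section 9.2.5.4 carries the CCO guidance over to the case-coverage design.

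SARS-CoV-2 appears in 9.2.5.5 as a time-varying confounder. It is handled through calendar time, or through individual infection data in the SCRI and CCO. For the SCRI the section concedes: "It is anticipated that not all hospitals will be able to collect information regarding individual-level infections for adjustment in the SCRI design". For the case-coverage design, 9.6.2 states: "The model will include only an intercept with no covariate". Neither the sensitivity analyses (9.6.5) nor the limitations (9.8) mention protection that changes with time since vaccination.

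**The concern.** The protocol treats circulating infection as something outside the vaccine that happens to vary over time. For an outcome that SARS-CoV-2 causes, however, the vaccine itself changes the event rate by preventing the infection, and it does so progressively after the dose. The first days of the risk window are unprotected. The SCRI control window and the CCO comparison window both represent time when protection is established. A vaccine that only prevents COVID-19 would then show a ratio above 1.

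Calendar-time terms cannot remove this, because protection follows time since vaccination and not the date. Table 2 also uses the SCRI as the secondary check on the CCO or the case-coverage design. On this mechanism all three err upward, so agreement between them would not reassure.

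**Working it through.** **Inputs from the protocol.** SCRI risk days 1-42 and control days 51-92 (Figure 3-1). CCO exposure 1-21 and comparison 50-70 days before the event (9.2.5.3). Table 3: 69 cases for 80% power at relative incidence 2 with half the observation time in the risk interval. Figure 3-1 has that ratio: 42/(42+42) = 50%.

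**Inputs assumed, not in the protocol.** No direct vaccine effect; constant infection pressure and, for the CCO, constant vaccination propensity; days 1-14 unprotected, then full protection; VE 70% or 90%; f = share of cases caused by SARS-CoV-2 in the absence of protection.

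**The plan's own figure first.** Standard signed-root sample-size formula for self-controlled case series, two-sided 5%, r = 0.5, b = ln 2:
- e^b·r + 1 − r = 1.5 and p = 1/1.5 = 0.667
- A = 2[0.667 × 0.693 − ln 1.5] = 0.1133
- B = (0.4805/0.1133) × (0.5/2.25) = 0.943
- n = (1.960 + 0.842 × √0.943)² / 0.1133 = 68.1, rounded up to 69

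This agrees with Table 3. The other 14 rows also reproduce, so the sample sizes are not in question.

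**Null ratio.** With u the unprotected fraction of the risk window:

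ratio = [f(u + (1−u)(1−VE)) + (1−f)] / [f(1−VE) + (1−f)]

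u = 14/42 for the SCRI and 14/21 for the CCO or case-coverage windows. Worked example, SCRI, f = 1, VE 90%: (0.333 + 0.667 × 0.1)/0.1 = 0.4/0.1 = 4.0.

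| f | SCRI, VE 70% / 90% | CCO, VE 70% / 90% |
|---|---|---|
| 0.1 | 1.03 / 1.03 | 1.05 / 1.07 |
| 0.5 | 1.18 / 1.27 | 1.36 / 1.55 |
| 1.0 | 1.78 / 4.00 | 2.56 / 7.00 |

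**Gradual onset instead of a step.** Let protection rise linearly from day 10 to day 28, with the Figure 3-1 windows. At f = 1 the null rate ratio is 1.44, 2.03 and 4.96 for VE 50, 70 and 90%. With Table 3's 69 cases (exact binomial, likelihood-ratio test at two-sided 5%), the chance of a significant finding of harm is 33%, 83% and about 100%, against 2.7% under no bias. At f = 0.5 the ratios are 1.15 to 1.36 and the chance is 9 to 25%. At f = 0.1 it is 3 to 4%.

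**Short windows.** Where "the outcome of interest has a risk interval of 0 to 7 days" and control days are 8-15, the f = 1 ratio is 1.0 to 1.1 if protection rises over days 10-28 or 14-35. It reaches 1.45 to 2.29 if protection rises over days 7-14.

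**Infection as a covariate.** In a CCO simulation with f = 0.5 and VE 90%, a yes/no infection term cut the odds ratio from 1.35 to 1.05. The crude value differs from the table above, so only the size of the reduction should be read. If every case is infected in the exposure window and none in the comparison window, the infection term separates completely and the vaccine odds ratio cannot be estimated.

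**The case against.** Much can be said for the plan.

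- **The table is preliminary and the windows are examples.** Sections 9.1 and 9.2.5.3 leave the design and windows for each outcome to the investigator. This stands and lowers the severity. But a plain tick is what users of a template will carry forward, and nothing prompts them to look for this problem.
- **Infection adjustment exists.** Section 9.2.5.5 names SARS-CoV-2 and gives infection its own risk window in the SCRI and a per-window status in the CCO. Section 9.6.5 offers an analysis restricted to sites with confounder data. This stands for partly infection-caused outcomes. A reader might infer that most sites will lack the data in both designs. The text says only that not all hospitals will have them, and ties this to missing post-discharge data in the SCRI; the CCO windows all precede the event.
- **The case-coverage offset could in principle carry infection status**, since reference strata are matched on an open list of confounders. That is true, but 9.2.5.4 expects even basic stratified vaccination data to be unavailable for most sites.
- **People with symptoms may defer vaccination**, which removes infection-caused events from the first days. If deferral halves them on days 1-14, the SCRI ratio falls to 1.05-1.12 at f = 0.5 and 1.2-2.3 at f = 1. The bias shrinks but remains.

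Two stronger readings are tempting. One is that every ticked outcome that SARS-CoV-2 can cause is affected, including coagulation disorder, acute cardiovascular injury and chilblain-like lesions. The protocol gives no infection share for these, and at small shares the bias is negligible. The other is that the protocol contradicts itself by rejecting enhanced disease, whose note says "Requires unvaccinated comparator to identify whether disease is" enhanced. That note concerns recognising enhancement, which is a different reason.

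**Conclusion.** The point holds for MIS-C, ARDS and any other outcome with a substantial SARS-CoV-2 share. Under the protocol's own example windows the bias is upward in all three designs, and the protocol does not address it.

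With the step at day 14 and VE 70 to 90%, it runs from about 1.2-1.3 (SCRI) and 1.4-1.5 (CCO) when half the cases are infection-caused to 1.8-4.0 and 2.6-7.0 when all are. It is negligible, about 1.03 to 1.07, at a share of 10% or less, and can be small for very short windows. VE, its onset and the share are assumptions, and so is the premise that SARS-CoV-2 causes most MIS-C and many ARDS cases.

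A false signal is therefore a risk for certain outcomes and not a certainty across the table. Nor does it follow that infection-free cases must be the primary analysis for every outcome: that restriction selects on an event after vaccination and loses cases where the bias is trivial.

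**What to change.** 1. In the case-ascertainment eCRF (9.2.4), record the SARS-CoV-2 test result and date at onset and over a prespecified look-back, from the chart already opened for adjudication.
2. In 9.6.5, for MIS-C, ARDS and any outcome with a substantial SARS-CoV-2 share, prespecify in each design an analysis restricted to cases without SARS-CoV-2 infection in the look-back. Report it beside the all-case result. State that a raised all-case estimate will not be read as vaccine harm unless it persists there.
3. In Table 4-1, change the tick to O for ARDS and to O or X for MIS-C. Give each its own note that protection against the causal infection differs between the windows. Describe the bias in 9.8.

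The cost is a small eCRF addition (tests done before admission may be harder to obtain), one extra analysis and two table entries. The restricted analysis will have fewer cases, untested infections will remain misclassified, and it conditions on a post-vaccination event, which should be stated when it is reported.
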